9.4 INTERIM MONITORING & ANALYSES

A DMC Charter will be drawn up that describes the membership of the DMC, terms of reference, decision-making processes, and the timing and frequency of meetings. The DMC will meet around the time the trial starts (without reviewing any data) to ensure they are familiar with its design and conduct. They will formally review data halfway through planned recruitment. They may call

additional meetings at any time at their discretion. In addition, SAEs will be sent weekly during the trial to the DMC.

The DMC can recommend premature closure or reporting of the trial, or that recruitment to any randomised group be discontinued or modified. Such recommendations would be made if, in the view of the DMC, there is an unacceptable rate of adverse reactions. There will be no early stopping for efficacy because this pilot trial is powered only to detect differences in skin bacterial load, not clinical efficacy outcomes. See Section 13.2 for details on DMC membership.

9.5 ANALYSIS PLAN (BRIEF)

The analyses will be described in detail in a full Statistical Analysis Plan. This section summarises the main issues.

The primary analysis population is intention-to-treat, including all randomised babies, regardless of treatment received. This corresponds to estimating the impact of the effectiveness of the treatments. However, in secondary analyses we will also use inverse-probability weighting methods to adjust for deviation from randomised strategy, which is a more efficient approach than defining a per-protocol population.³⁹ Loss-to-follow up is expected to be low given that expected length of hospital stay under 7 days is an exclusion criteria. Therefore, most babies should have baseline and two subsequent swabs on their allocated regimen. Missing swabs will be monitored and babies without baseline and two post-baseline swabs will be replaced to maintain power. However, all baseline and post-baseline results will be included in analyses.

Analysis of the co-primary endpoints will compare within-individual differences over time across randomised arm to maximise the information gained from the trial. Analysis will use linear mixed-models, with individual as a random effect, will adjust for baseline values of each outcome, and use Normally distributed errors. Analysis will be both frequentist, enabling straightforward comparison between arms (primary analysis since sample size is based on this), and Bayesian, enabling estimation of the probability that one arm is truly superior to another. This is more powerful when sample sizes are small as use of priors provides additional information. Sensitivity analysis to prior assumptions will be performed using optimistic, non-informative and sceptical priors. Change from baseline to the single closest sample 48h post randomisation will also be done as a sensitivity analysis.

The effect of each treatment arm will be assessed within a single model with each factor being fitted independently as a factor, and not as a continuous variable. Comparison of main effects within arms will be assessed using the estimate and 95% confidence interval of the comparison of differences between factors and in comparison, to control. As this is a pilot trial, the sample size was not powered to robustly detect interactions between chlorhexidine concentrations/frequencies and emollients and so we will not test these formally, but will use exploratory analyses to assess whether there is any evidence supporting individual interactions testing each one, one at a time. As this is a pilot trial and the two co-primary outcomes capture different aspects (efficacy and safety) there will be no adjustment for multiple testing, nor for the two different bacterial load outcomes since we expect a reduction in colonisation on the skin, but potentially no change in colonisation peri-rectally.

Similar mixed models will be used to analyse change in skin temperature after vs before each application, including individual as a random effect, the change in temperature as the outcome and the pre-application (baseline) temperature as a factor. Acquisition and loss of each species will be analysed as a binary outcome variable, compared with baseline, in the relevant population (those without the species of interest at baseline, or with the species of interest at baseline, respectively).

Presence/absence of each species at each assessment will also be compared between randomised groups using mixed models, again with individual as a random effect, and with baseline presence as a factor.

Frequency of SAEs will be tabulated by randomised group, and compared using exact logistic models (or time-to-event models if AEs occur in >10% of the trial population overall). SAEs will also be tabulated by grade. Similar analyses will be conducted for the AEs in Appendix II.

A Statistical Analysis Plan will be written and approved by the Trial Management Group (TMG) and the DMC before the first interim analysis is reviewed by the DMC.

10 REGULATORY & ETHICAL ISSUES

10.1 COMPLIANCE

10.1.1 REGULATORY COMPLIANCE

The trial complies with the principles of the 1996 version of the Declaration of Helsinki.

It will also be conducted in compliance with the approved protocol, the principles of ICH Good Clinical Practice (GCP) as laid down by the ICH topic E6 (R2).

10.1.2 SITE COMPLIANCE

The site will comply with the above and also with applicable national regulations. An agreement will be in place between the site and SGUL (Sponsor), setting out respective roles and responsibilities (see Section 13 - Finance).

The site will inform the MRC CTU and SGUL as soon as they are aware of a possible serious breach of compliance, so that they can report this breach if necessary as per relevant regulatory requirements. For the purposes of this regulation, a 'serious breach' is one that is likely to affect to a significant degree:

- The safety or physical or mental integrity of the subjects in the trial, or
- The scientific value of the trial

10.1.3 DATA COLLECTION & RETENTION

CRFs/worksheets, clinical notes and administrative documentation should be kept in a secure location (for example, locked filing cabinets in a room with restricted access) and held for a minimum of 25 years after the end of the trial. During this period, all data should be accessible, with suitable notice, to the competent or equivalent authorities, the Sponsor, and other relevant parties in accordance with the applicable regulations. The data may be subject to an audit by the competent authorities. Medical files of trial participants should be retained in accordance with the maximum period of time permitted by the hospital, institution or private practice.

10.2 ETHICAL CONDUCT

10.2.1 ETHICAL CONSIDERATIONS

The main ethical concern in this trial relates to potential skin damage, which could lead to infection, and potentially to scarring of the skin. Chlorhexidine is widely used for skin disinfection in neonates. The main risk is with high concentrations (>2%) in extremely low birth weight/preterm neonates (<1kg/<28 weeks), among whom skin reactions have been observed, particularly when chlorhexidine is combined with alcohol. The MHRA accordingly warns about use of high concentrations in this group. Hypothermia has also been observed after skin cleansing with chlorhexidine on the first day of life. This trial will exclude neonates less than 1kg at enrolment and below 28 weeks' gestational age, and start application 1-6 days after birth, which will minimise, although not entirely eradicate these risks. However, close and regular monitoring of the skin with a standardised skin condition scoring system, and temperature checking after application will allow chlorhexidine to be discontinued at the discretion of the local clinician.

Neurotoxicity, which is a theoretical concern, has never been reported in neonates despite widespread use of chlorhexidine, and large studies including daily application of chlorhexidine 4% to the cord, which has been associated with higher blood levels of chlorhexidine than skin application.

Given the absence of known toxicity even in the context of detectable blood chlorhexidine levels, this trial will follow other previous large studies in not measuring blood levels, but will assess neonates for any clinical signs of neurological disturbance (see Appendix II).

Importantly, safety concerns are one the main justifications for this pilot, in order to identify the safest but most effective regimen which could be tested in a larger trial aiming to reduce neonatal sepsis and mortality.

Confidentiality of the babies and their parents/care-givers will be maintained throughout the trial. Data submitted on CRFs/worksheets to trial sites and CTU, will be identified only by the trial number and date of birth (including random check letters to improve accuracy of identification). Date of birth is essential given all participants will be under 1 month of age.

Parents and/or carers will be informed fully of known risks and possible benefits by means of a patient information sheet, and this will be reinforced by discussions with the trial research teams at the individual sites prior to enrolment.

For the staff involved in the trial, any risk is expected to be minimal and related to skin irritation with chlorhexidine, or in very rare cases (<1/10,000 as per summary product characteristics), allergic responses to chlorhexidine. Staff with a previous history of sensitivity to chlorhexidine will not take part in application of chlorhexidine.

10.2.2 ETHICAL APPROVALS

Before initiation of the trial at clinical sites, the protocol, all informed consent forms, and information materials to be given to the families will be submitted to an ethics committee for approval. Any further amendments will be submitted and approved by the ethics committee.

The rights of the parent/carer to refuse for their baby to participate in the trial without giving a reason must be respected. After the baby has entered into the trial, the clinician remains free to give alternative treatment to that specified in the protocol, at any stage, if he/she feels it to be in the best interest of the baby. The reason for doing so, however, should be recorded; the baby will remain within the trial for the purpose of follow-up and for data analysis by the treatment regimen to which they were randomised.

10.3 TRIAL CLOSURE

End of trial is defined as 12 months after the last scheduled follow-up visit of the last randomised baby. This is to ensure sufficient time for data submission, data cleaning, verification of queries, database lock and final analysis. Each site will be closed once data cleaning is completed at that site, and the ethics committee and any relevant regulatory authorities will be informed.

11 INDEMNITY

The Sponsor of the trial is St George's, University of London. In consideration of the agreement by the Principal Investigator at each site to supervise the trial, the sponsor undertakes to indemnify the Principal Investigator at each site and the institutions which participate in the trial and their employees and agents in respect of any claims made against them by any third party which arises out of or as a result of the supervision or conduct of the trial (including any claim arising in respect of the technical procedures described in the protocol which babies would not have been exposed to but for their participation in the trial). Full details of the Indemnity agreement are given in a separate document. Cover against claims arising from medical negligence is not included.

12 FINANCE

The NeoCHG trial is funded by the MRC/NIHR/DfID/Wellcome Joint Global Health Trials Call 9 – Trial Development Grant. The Medical Research Council also provides core support to the MRC CTU.

13 OVERSIGHT & TRIAL COMMITTEES

There are several groups involved with the oversight of the trial, detailed below.

13.1 TRIAL MANAGEMENT GROUP (TMG)

A Trial Management Group (TMG) will be formed comprising the Chief Investigator, other lead investigators (clinical and non-clinical) and members of the MRC CTU. The TMG will be responsible for the day-to-day running and management of the trial. It will meet approximately every other month. The full details can be found in the TMG Charter.

13.2 INDEPENDENT DATA MONITORING COMMITTEE (DMC)

An independent Data Monitoring Committee (DMC) will be formed. The Chair will be [name] (KEMRI Wellcome Trusts, Kilifi, Kenya) and the independent member will be [name] (Division of Infectious Diseases at Children's Hospital of Philadelphia). The DMC will be the only group who sees the confidential, accumulating data for the trial. Reports to the DMC will be produced by the MRC CTU statistician(s). The DMC will meet at the beginning of trial to become familiar with the protocol, then approximately halfway through expected recruitment. The DMC will consider data using the statistical analysis plan (see Section 9.5) and will advise the TMG. The DMC can recommend premature closure or reporting of the trial, or that recruitment to any randomised arm be discontinued.

Further details of DMC functioning, and the procedures for interim analysis and monitoring are provided in the DMC Charter.

13.3 ROLE OF STUDY SPONSOR

St George's, University of London, is the Sponsor and delegates this responsibility to the MRC CTU at UCL to oversee the implementation of the trial by ensuring that arrangements are put into place for adequate management, monitoring, analysis and reporting of the trial.

14 PATIENT AND PUBLIC INVOLVEMENT

There are no existing patient and public involvement (PPI) groups for premature babies or those admitted to neonatal units at participating sites. Furthermore, this is a sensitive area given the acutely sick nature of babies admitted to these units and the high risks of poor outcomes. Within this pilot trial, there is no specific resource to set up formal patient and public involvement, but we will explore with the parents/carers of babies recruited into this pilot trial their potential interest in being involved in future engagement around a larger trial, particularly in terms of the potential acceptability of the intervention, and differing cultural practices around use of skin products and emollients in premature newborn babies. Therefore, this pilot trial will assess the feasibility of establishing parent/carer groups and identifying possible parent/carer representatives for a future larger trial.

15 PUBLICATION AND DISSEMINATION OF RESULTS

The TMG is responsible for access to the data and bacterial isolates generated from the NeoCHG trial; NeoCHG trial data are not the property of individual participating investigators or healthcare facilities where the data were generated.

- Publications include papers (including abstracts) for presentation at national and international meetings, as well as the preparation of manuscripts for peer-reviewed publication. In order to avoid disputes regarding authorship, it is important to establish a consensus approach that will provide a framework for all publications derived in full or in part from this clinical trial. The following approach is derived from the Lancet and from the publication policies used in other clinical trials coordinated by the MRC CTU at UCL.
- All publications are to be approved by the TMG before submission for publication. Any
 publication arising before the end of the trial (not by randomised groups) will also be
 approved by the DMC in order to ensure that the primary objective of the trial (the
 randomised comparison) is not compromised. The TMG will resolve problems of
 authorship and maintain the quality of publications.
- In line with MRC policy that the results of publicly-funded research should be freely available, manuscripts arising from the trial will, wherever possible, be submitted to peer-reviewed journals which enable Open Access via UK PubMed Central (PMC) within six months of the official date of final publication.
- For all publications, the TMG will nominate a chairperson or approve an individual's request to chair a manuscript writing committee. The chair will usually be the primary or senior author. The chairperson is responsible for identifying fellow authors and for determining with that group the order of authorship that will appear on the manuscript. The TMG will resolve any problems of authorship and maintain the quality of publications.
- The TMG will maintain a list of investigators to be presented in an appendix at the end of the paper. This list will include investigators who contributed to the investigation being reported but who are not members of the writing committee, together with all relevant expert advisors and members of the DMC. All families who participated in the trial will be thanked as a group (not by name). In principle, sub-study reports should include all investigators for the main trial, although in some instances where a smaller number of investigators have made any form of contribution, it may be appropriate to abbreviate the listing. All headline authors in any publication arising from the main trial or substudies must have a made a substantive academic or project management contribution to the work that is being presented. "Substantive" must be defined by a written declaration of exactly what the contribution of any individual is believed to have been. In addition to fulfilling the criteria based on contribution, additional features that will be considered in selecting an authorship group will include the recruitment of babies who contributed data to any set of analyses contained in the manuscript and/or the conduct of analyses (laboratory and statistical), leadership and coordination of the project in the absence of a clear academic contribution.
- The data derived from this clinical trial are considered the property of the Sponsor. The presentation or publication of any data collected by the participating investigators on

babies entered into this trial is under the direct control of the TMG (and the DMC before the end of the trial). This is true whether the publication or presentation is concerned directly with the results of the trial or is associated with the trial in some other way. However, although individual participating investigators will not have any inherent right to perform analyses or interpretations or to make public presentations or seek publication of any of the data other than under the auspices of and with the approval of the TMG (and the DMC before the end of the trial), they will be encouraged to develop sub-studies or propose analyses subject to the approval by the TMG (and the DMC before the end of the trial). Any requests for access to raw data will be welcomed as long as they are scientifically valid and do not conflict with the integrity of the trial or ongoing analyses by the trial team.

Outcome data by randomised group will not be revealed to the participating investigators until the data collection phase and primary full analysis of the trial has been completed. This policy safeguards against possible bias affecting the data collection. The DMC will be monitoring the outcome results and may recommend that the trial be stopped for safety reasons.

16 DATA AND/OR SAMPLE SHARING

Data will be shared according to the MRC CTU's controlled access approach, based on the following principles:

- No data should be released that would compromise an ongoing trial or study.
- There must be a strong scientific or other legitimate rationale for the data to be used for the requested purpose.
- Investigators who have invested time and effort into developing a trial or study should have a period of exclusivity in which to pursue their aims with the data, before key trial data are made available to other researchers.
- The resources required to process requests should not be under-estimated, particularly successful requests which lead to preparing data for release. Therefore, adequate resources must be available in order to comply in a timely manner or at all, and the scientific aims of the study must justify the use of such resources.
- Data exchange complies with Information Governance and Data Security Policies in all of the relevant countries.

Data will be available for sharing after the trial has reported the primary outcome. Researchers wishing to access trial data should contact the TMG in the first instance.

17 PROTOCOL AMENDMENTS

List of changes from v.1.0 (6th March 2020) to v.2.0 (29th November 2021):

- Trial registration (p6): Inclusion of ISRCTN number
- MRC CTU Staff (p8): Update to MRC CTU trial team (addition of [name])
- Trial Schema (p11), Summary of trial (p13), Section 9.2.2 Secondary outcome measures (p42): Addition of the acquisition & loss of *Pseudomonas aeruginosa* as a secondary outcome measure
- Trial Schema (p14), Section 3.3 Number of patients (p26): Removal of reference to recruitment targets of 91 babies per site
- Trial Assessment schedule (p15), Section 6.1 Trial assessment schedule (p34): Removal of collection of intrapartum antibiotic history as part of baseline data collection
- Section 3.1 Patient inclusion criteria (p26): Clarification that day 1 is defined as the second day of life, to align with section 1.4.1
- Section 5.3.1 Control group: Products (p32): Correction that control group receives assessment on alternate working days, not daily, which also aligns with section 6.1
- Section 7.3.3 Investigator assessment: Causality (p38): Correction of table numbers (from 3 to 2)
- Section 9.4 Interim monitoring & analyses (p43): Clarification that the DMC receives SAEs (not only SARs) on a weekly basis (not in real time)
- Section 13.2 Independent Data Monitoring Committee (DMC) (p49): Update to DMC committee members: removal of [name] as DMC chair; addition of [name] as DMC chair and of [name] as DMC member

APPENDIX I SKIN SCORE ASSESSMENT

Skin toxicity score

Adapted from Lund & Osborne.³¹ The skin should be scored on each of the three domains (dryness, erythema and skin breakdown), and then the total score is the sum of the three components (minimum score 0, maximum score 12).

Highest grade from:

Grade 1 = Score of \geq 1 in \geq 2 categories

Grade 2 = Score of \geq 2 in \geq 2 categories

Grade 3 = Score of \geq 3 in \geq 2 categories

Grade 4 = Score of \geq 4 in \geq 2 categories

Score	Description
Domain 1	Dryness
0	Normal
1	Dry skin +/- scaling <50%
2	Dry skin + scaling >50% +/- cracking/fissures <50%
3	Very dry + cracking / fissures >50%
4	Very dry + cracking / fissures >75%
Domain 2	Erythema
0	Normal
1	Erythema <25%
2	Erythema 25-50%
3	Severe Erythema 50-75%
4	Severe Erythema >75%
Domain 3	Skin breakdown
0	Normal
1	Skin breakdown/ulceration/vesicles <5%
2	Skin breakdown/ulceration/vesicles 5-25%
3	Skin breakdown/ulceration/vesicles 25-50%
4	Skin breakdown/ulceration/vesicles >50%

Figure 3: Skin Affected Area assessment

Modified Lund and Browder chart for estimation of BSA burn involvement in infants and children. (From Harwood-Nuss A, Wolfson A, Linden C. *The clinical practice of emergency medicine*. Philadelphia: Lippincott-Raven; 1996:1207⁴⁰

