3.2 PATIENT EXCLUSION CRITERIA

- 1. Poor skin condition (skin score of 2 or more in any of three domains (see Appendix I)) at the time of enrolment
- 2. Known congenital or acquired skin disorder or defect at time of enrolment
- 3. Anticipated length of hospital stay <7 days
- 4. Chlorhexidine or emollient application determined inappropriate in the opinion of the enrolling clinician

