5.2.1.2 Dose Interruptions & Discontinuations

Doses and concentrations will not be modified after the baby has been randomised. Consideration of temporary or permanent discontinuation of chlorhexidine should be made at the discretion of the treating clinician in the following circumstances:

- Hypothermia < 36.0C immediately before chlorhexidine application
- Skin score >2 in any category immediately before chlorhexidine application (see Appendix I)
- Neurological disturbance

When chlorhexidine is temporarily stopped for any reason, an assessment will be performed at the time of the next scheduled application and the clinician will determine whether it should be restarted.

Treatment interruptions and discontinuation should be recorded as appropriate on the trial CRFs/worksheets.

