9.2 OUTCOME MEASURES

9.2.1 CO-PRIMARY OUTCOME MEASURES

- Skin bacterial load change in colony forming units (CFUs) in the nose (1 swab), cervical skin folds and umbilicus (1 pooled swab), and peri-rectal area (1 swab) from randomisation (before chlorhexidine application) to D3+/- 1 day and D8 +/- 3 days microbiology data collection (efficacy).
- Modified neonatal skin condition score (see Appendix I) used before each application of chlorhexidine, or alternate working days in controls (safety). The primary analysis of this outcome will consider the absolute score. Secondary analysis of this outcome will consider graded toxicity (see Appendix I).

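### Appendix I gives a skin toxicity grade only when two domains are affected, so severe damage confined to one domain receives no grade while two mild signs receive Grade 1

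*Protocol*

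**What the plan says.** Appendix I scores three domains (dryness, erythema, skin breakdown) from 0 to 4 and sums them to a total with "minimum score 0, maximum score 12". It then derives a toxicity grade, introduced by "Highest grade from" and running from "Grade 1 = Score of \geq 1 in \geq 2 categories" through "Grade 2 = Score of \geq 2 in \geq 2 categories" to "Grade 4 = Score of \geq 4 in \geq 2 categories". No grade can be reached through one domain, and breakdown has no override.

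The grade has two uses. Section 9.2.1 makes the absolute score the primary analysis of the safety co-primary outcome and adds: "Secondary analysis of this outcome will consider graded toxicity (see Appendix I". Section 7.1.2 sends the grading of skin damage to Appendix I, separately from the general adverse event scale in Appendix II, which has no skin row.

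Two other rules use the same domain scores and act on one domain alone. Section 3.2 excludes babies with "Poor skin condition (skin score of 2 or more in any of three domains". Section 5.2.1.2 lists, among the reasons to consider interrupting or stopping chlorhexidine, "Skin score >2 in any category immediately before chlorhexidine application".

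**The concern.** A toxicity grade should not fall as harm becomes more severe. Under a two-domain rule, extensive ulceration with no dryness or erythema ranks below slight dryness with slight redness. A baby who meets the single-category condition in section 5.2.1.2 can carry no skin grade at all.

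Section 10.2.1 names skin damage as the main ethical concern, and section 1.4.6 says the pilot will determine the regimen for a larger trial. A graded table is where a reader would look for uncommon severe skin events, because the primary analysis is a linear mixed model on the score (section 9.5) and compares average levels.

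The rule could also colour the emollient comparison. If emollient did no more than remove dryness, the grade could drop while breakdown stayed the same.

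**Working it through.** **Inputs.** Three domains, each 0 to 4, and the four grade definitions (Appendix I); the entry criterion of 2 or more in any domain (section 3.2); the condition of more than 2 in any category (section 5.2.1.2). Patterns are written (dryness, erythema, breakdown).

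**Reproducing the plan's figure.** Minimum total 3 × 0 = 0; maximum total 3 × 4 = 12. This agrees with Appendix I.

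**What the rule computes.** Grade *k* needs at least two domains at *k* or more, which is the same as the second-highest score being at least *k*. Taking the highest grade that qualifies, the grade equals the second-highest (median) of the three scores. Applying the rule to all 5³ = 125 patterns confirmed this for every one.

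**Examples.**

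| Pattern | Meaning | Total | Grade |
|---|---|---|---|
| (0,0,4) | breakdown >50% only | 4 | none |
| (0,4,0) | severe erythema >75% only | 4 | none |
| (4,0,0) | worst dryness only | 4 | none |
| (0,1,4) | breakdown >50%, erythema <25% | 5 | 1 |
| (1,1,0) | mild dryness, mild erythema | 2 | 1 |

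**Counts of patterns.**

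- Ungraded: normal skin plus 3 domains × 4 non-zero scores = 1 + 12 = 13. All 12 single-domain patterns are among them.
- At least one domain at 3 or 4 (the level in section 5.2.1.2): 125 − 3³ = 98.
- Of these 98, graded below 3 or ungraded: 3 × 2 × 3² = 54.
- Of these 98, Grade 1 or ungraded: 3 × 2 × 2² = 24.
- Of these 98, ungraded: 3 × 2 × 1 = 6, leaving 24 − 6 = 18 at Grade 1.
- At least one domain at 2 or more (the level in section 3.2): 125 − 2³ = 117, of which 3 × 3 = 9 are ungraded.

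**Emollient illustration (hypothetical).** If dryness alone is removed, (2,0,4) becomes (0,0,4). The grade goes from 2 to none with breakdown unchanged, while the total moves only from 6 to 4.

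**Worst-domain alternative.** If the grade is the highest domain score, only (0,0,0) is ungraded. The two rules agree when the top two scores are equal: Σ(3m + 1) for m = 0 to 4 = 35 patterns. They differ in 125 − 35 = 90.

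**The case against.** The strongest reply is that the grade is secondary. Under section 9.2.1 the primary safety analysis uses the absolute score, in which isolated breakdown above 50% counts 4 of 12, above the 2 of 12 for mild dryness plus mild erythema. This stands, and it limits the scope of the point. It does not repair the grade: a total of 4 also describes (2,2,0), so the total alone cannot identify severe single-domain damage.

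A reader might infer that a regimen causing skin injury could go forward unseen. The protocol does not support that. No section makes the choice of regimen depend on the grade table. Scores are taken before and after application (section 6.3), interruptions and discontinuations are recorded (section 5.2.1.2), serious events including skin damage are notified within 24 hours (section 7.2), and SAEs go weekly to the DMC (section 9.4). None of these uses the Appendix I grade.

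A reader might also take 54 of 98, or 6 of 98, as a misclassification rate. It is not one. Each pattern is counted once, including patterns that may be very unlikely, and section 1.4.1 describes skin damage in similar populations as very rare.

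Sections 3.2 and 5.2.1.2 are entry and management rules, while Appendix I classifies outcomes. They may differ in threshold without strictly contradicting each other. What stands is that the same domain scores are acted on singly in those two places but can leave no trace in the grade.

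Two points of wording also stand. Appendix I names no Grade 0 for skin, so placing ungraded damage with normal skin is an inference about how a graded table would be laid out. The percentages appear to be shares of body surface, since the appendix refers to a body-surface chart.

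**Conclusion.** The point holds with limited scope. As written, the Appendix I grade is the second-highest domain score, so it can rank extensive isolated ulceration or erythema below two mild signs. All 12 single-domain patterns are ungraded, including 6 of the 98 with a domain at 3 or 4. The graded secondary analysis of the safety co-primary outcome and the grading of skin damage under section 7.1.2 are affected, and nothing else in the protocol corrects them. The primary safety analysis and serious event reporting are unaffected.

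The conclusion rests on the four grade lines as printed and on ungraded babies being tabulated with normal skin. How many babies would be affected cannot be derived from the protocol. Because grades can be recalculated from the domain scores, the defect is reversible. It should be corrected before graded safety tables are produced, but it does not threaten the trial's primary result.

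**What to change.** For outcome reporting only, redefine the grade in Appendix I so that the worst single domain can set it: grade *k* if any domain scores *k* or more, taking the highest. Keep the two-domain version as a sensitivity table, and tabulate the breakdown domain separately by arm. State in which category babies who meet no grade are counted.

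The eligibility and discontinuation texts should stay unchanged under this edit. The sponsor should reconcile the two-domain grade with the single-domain criteria in sections 3.2 and 5.2.1.2, for instance by stating that they serve different purposes. No clinical threshold is proposed here.

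The cost is one changed definition and a recalculation from the domain scores that make up the total. The downside is that mild isolated dryness would become Grade 1 and isolated severe dryness would be graded high (a dryness score of 4 would be Grade 4). The separate breakdown table and the two-domain sensitivity table let a reader see when dryness drives the grades.
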